A subject achieves LLDAS response if all of the following criteria are met:

1. hSLEDAI ≤ 4 with no activity in major organ systems (renal [proteinuria, haematuria, pyuria, urinary casts], central nervous system (CNS) [seizure, psychosis, organic brain syndrome, cranial nerve disorder, CVA], cardiopulmonary [pericarditis, pleurisy], vasculitis, fever) and no haemolytic anaemia or gastrointestinal activity in BILAG
2. no new lupus disease activity (i.e. no new descriptor scores in hSLEDAI, and no new activity in haemolytic anaemia or gastrointestinal domain in BILAG) compared with the previous assessment
3. PGA (scale 0-3) ≤ 1
4. Current prednisolone (or equivalent) dose ≤ 7.5 mg/day
5. Well tolerated standard maintenance doses of immunosuppressive drugs and approved biological agents (i.e. no increase or initiation of immunosuppressive drugs).

BILAG Flare Index

The BILAG flare index will be derived from BILAG 2004, as measured by BILAG score designation of “worse” or “new” resulting in a B score in ≥ 2 organs or an A score in ≥ 1 organ (Gordon et al, 2003) compared to previous available assessment.

SELENA-SLEDAI Flare Index

A mild or moderate flare is defined as satisfying 1 or more of the following compared with previous assessment:

- a. change in SELENA-SLEDAI instrument score of 3 points or more points (but not more than 12)
- b. new or worse discoid, photosensitive, lupus profundus, cutaneous vasculitis, or bullous lupus, nasopharyngeal ulcers, pleuritis, pericarditis, arthritis, or fever (SLE)
- c. increase in prednisone, but not to ≥ 0.5 mg/kg/day
- d. added nonsteroidal anti-inflammatory drugs (NSAIDs) or hydrochloroquine for SLE activity
- e. ≥ 1 increase in PGA score but not to more than 2.5

A severe flare is defined as satisfying 1 or more of the following compared with previous visit:

- a. change in SELENA-SLEDAI instrument score to greater than 12
- b. New or worsening CNS-SLE, vasculitis, nephritis, myositis, platelet count $< 60 \times 10^9$ cells/L, or hemolytic anemia (hemoglobin level < 70 g/L or decrease in hemoglobin level > 30 g/L requiring double prednisone or prednisone increase to > 0.5 mg/kg/day or hospitalization)
- c. increase in prednisone to > 0.5 mg/kg/day
- d. new cyclophosphamide, azathioprine, mycophenolate mofetil, or methotrexate
- e. Hospitalization for SLE activity
- f. increase of PGA to ≥ 2.5

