To distinguish between mild and moderate flare an additional question, “Status”, was added to the classic instrument. Based on the investigator’s clinical judgement, the flare is to be classified as one of the following 4 options: No Flare,

[figure not shown]
Mild Flare, Moderate Flare, Severe Flare. SELENA-SLEDAI flare data collected in ClinicalLink were transcribed to Rave and hence will be excluded from analyses to avoid duplicate records.

Annualized Flare Rate

The annualized flare rate will be calculated as the number of flares divided by the flare exposure time in days multiplied by 365.25.

Systemic Lupus International Collaborating Clinics/American College of Rheumatology Damage Index (SDI)

The SDI global score will be calculated as the sum of the damage scores (0-47) from 12 organ systems with the following possible scores: ocular (0-2), neuropsychiatric (0-6), renal (0-3), pulmonary (0-5), cardiovascular (0-6), peripheral vascular (0-5), gastrointestinal (0-6), musculoskeletal (0-7), skin (0-3), premature gonadal failure (0-1), diabetes (0-1) and malignancy (0-2).

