In case of partially missing, missing laboratory items (e.g. UPCR, creatinine, etc.), **nephrotic syndrome or urinary sediment** will be imputed using LOCF if the previous visit is not missing; other missing items (e.g. active nephritis, Coombs' test positive, etc.) will be imputed as 'No' or 'Not Present'.

Baseline BILAG will not be carried forward to missing post-baseline BILAG.

The BILAG organ domain scores will be based on the non-missing and imputed components. If the non-missing and imputed components are not sufficient to identify the organ domain score, worst scenario approach will be used to determine the BILAG organ domain scores.

PGA

Missing post-baseline PGA score will be imputed using LOCF if the previous analysis visit is not missing. Baseline PGA will not be carried forward to missing post-baseline PGA.

SRI-4, BICLA and LLDAS

The criteria for SRI-4, BICLA and LLDAS responses will be evaluated based on the non-missing and imputed PGA, hSLEDAI and BILAG data. If any criteria based on the non-

missing and imputed PGA, hSLEDAI and BILAG data cannot be evaluated, then the subject will be considered non-responder.

BILAG Flare index

BILAG flare index will be evaluated based on BILAG scores. In case of partially missing BILAG assessment, imputed BILAG scores will be used. In case of completely missing BILAG assessment, BILAG flare index will remain missing.

Tender and Swollen Joint Counts

If a joint is excluded (non-evaluable, missing or not done), the joint counts will be prorated based on the algorithm described below.

[figure not shown]
Prorated Joint Counts: If at least half but not all joints are evaluable (at least 14 joints for the total 28 joint count, at least 11 joints for the 22 hands and wrists joint count) then the observed prorated tender or swollen joint count will be calculated. The prorated scores will be adjusted based upon the number of evaluable joints: the counted score will be multiplied by 28 (for total) or 22 (for hands and wrists) as applicable and divided by the number of joints evaluated. If less than half of the joints are evaluable, the number of tender or swollen joints is missing. For example, if only 25 of the 28 joints are assessed at a visit and 10 of those 25 are tender and 8 of those 25 are swollen, the prorated total joint counts are:

Tender: $(10/25) * 28 = 11.20$,

Swollen: $(8/25) * 28 = 8.96$.

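### Where LOCF is unavailable, the SAP's worst-scenario BILAG score can enter the BILAG flare rate as an A flare that nobody observed

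*SAP*

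**What the plan says.** SAP 8.3 handles a partly missing BILAG form in steps. Missing laboratory items, nephrotic syndrome and urinary sediment "will be imputed using LOCF if the previous visit is not missing; other missing items" are set to absent. A separate line adds: "Baseline BILAG will not be carried forward to missing post-baseline BILAG". Then: "If the non-missing and imputed components are not sufficient to identify the organ domain score", the "worst scenario approach will be used to determine the BILAG organ domain scores". The SAP does not define worst scenario further.

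The BILAG Flare index paragraph of the same section treats two cases differently. For a form with gaps, the rule is: "In case of partially missing BILAG assessment, imputed BILAG scores will be used". A form that is absent altogether gets another rule: "In case of completely missing BILAG assessment, BILAG flare index will remain missing".

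SAP 5.6 defines a BILAG flare as a worse or new designation "resulting in a B score in ≥ 2 organs or an A score in ≥ 1 organ", compared with the previous available assessment. The rate follows from this: "The annualized flare rate will be calculated as the number of flares divided by the flare exposure time in days multiplied by 365.25". SAP 5.1 counts exposure time from study day 1 to the last flare assessment. The annualized BILAG flare rate is a secondary endpoint, summarised descriptively by randomized arm (SAP Table 9-2).

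**The concern.** A worst-case score is a cautious choice for a response endpoint such as SRI-4 or BICLA, where it can only take a response away. For an event count it works the other way: it adds an event with no observation behind it. The SAP feeds the same imputed domain scores to both kinds of endpoint.

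Partial and complete missingness are also treated in opposite directions. A subject who attends but has no usable sample can gain a flare. A subject who misses the whole assessment cannot. What is at stake is the BILAG flare rate reported for each arm: part of it could reflect laboratory availability rather than lupus activity, and to a different degree in each arm if sample loss differs.

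**Working it through.** The documents give no figure for the effect of this rule, so there is nothing to reproduce. The check applies the Appendix B scoring to missing items and then applies the rate formula.

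**Step 1: when the worst scenario is reached.** With an observed previous post-baseline visit, LOCF repeats the earlier laboratory values and the domain can be scored. LOCF is unavailable at week 4, because the only earlier visit is baseline. It is also unavailable after a wholly missed visit, if a visit that was itself filled by LOCF still counts as missing; the SAP does not say.

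**Step 2: the grade.** Missing laboratory, nephrotic and sediment items are set to their worst value. Haemolysis, TTP, Coombs' test and active nephritis are set to absent, as SAP 8.3 directs. Everything else is normal.

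| Missing | Worst grade | Flare on its own? |
|---|---|---|
| Haemoglobin, white cells or neutrophils alone | Haematological B | No |
| Lymphocytes alone | Haematological C | No |
| Platelets alone, or whole blood count | Haematological A (platelets < 25 not excluded) | Yes |
| Urine protein, sediment, nephrotic syndrome or creatinine alone | Renal B (one A feature) | No |
| Whole urine sample (protein and sediment) | Renal A (two features) | Yes |
| Whole blood sample | Haematological A and renal B | Yes |

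A single B counts only if a second organ also reaches B. The A must also be worse than the previous available assessment. For platelets this will nearly always hold at week 4, since Protocol 6.2 (criterion 221) excludes platelets below 75 × 10⁹/L at screening.

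**Step 3: one false flare in one subject's rate**, 1 × 365.25 / exposure days:
- 365 days: 365.25 / 365 = 1.00 per year
- 169 days: 365.25 / 169 = 2.16 per year
- 85 days: 365.25 / 85 = 4.30 per year

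Short follow-up after early termination therefore magnifies an early false flare.

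**Step 4: effect on an arm.** Let q be the chance that an otherwise completed week 4 form has no usable sample in its analysis window, days 2 to 42 (SAP Appendix D). The documents do not give q. The addition to the arm rate is q × 365.25 / exposure days:

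| Assumed q | 365 days | 169 days |
|---|---|---|
| 2% | 0.02 | 0.043 |
| 5% | 0.05 | 0.108 |
| 10% | 0.10 | 0.216 |

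Against an assumed true rate of 0.3 to 0.5 flares per year (also not in the documents), the 365-day additions are 4–7%, 10–17% and 20–33%. Visits after a wholly missed one add a small part that is not quantified here.

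**Step 5: a wholly missed interior form.** The monthly windows from week 8 to week 48 are 28 days wide, and 28 / 365 = 7.7%. Take a subject with one flare elsewhere. The rate as written is 365.25 / 365 = 1.00. With the missed window taken out it would be 365.25 / 337 = 1.08. The missed form adds no flare, and its days remain in the denominator.

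**The case against.** The strongest objection is to the reading of a flare. The definition asks for a worse or new designation, and almost all haematological and renal items are values or yes/no entries that carry none. If a recorded designation is required, a worst-scenario laboratory grade creates no flare. This cannot be excluded. But it would also remove nearly all genuine cytopenic and renal flares, and it fits poorly with SAP 8.3, which bases the index on BILAG scores and directs that imputed scores be used. Judging domain scores against the previous available assessment is the more natural reading, and the point depends on it.

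A second objection is that q may be small. Appendix D accepts any visit in the window with data, including unscheduled ones, and Protocol Table 12-1 (footnote a) lets the sponsor approve local testing when central testing is unavailable. This stands, and it is why q is defined over the whole window.

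A reader might also infer more than the text supports:
- *That any missing blood or urine sample becomes a flare.* LOCF comes first, and most single missing items give one B.
- *That two missing samples in a row at attended visits create a flare*, adding about 12q² over the twelve later monthly visits. The LOCF condition concerns the previous visit, not the previous item. A visit that was attended without a blood count is not a missing visit, so this term is not supported.
- *That a wholly missed form is scored as no flare.* The index remains missing. A flare that persists is still picked up at the next assessment, because comparison is with the previous available one.
- *That a treatment contrast is diluted or biased.* SAP section 10 removes statistical comparisons. Equal false flares in all arms would leave an absolute difference unchanged, and no rate ratio is planned.

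**Conclusion.** The point holds in a limited form. Where LOCF is unavailable, the SAP as written can turn a missing platelet count, whole blood count or whole urine sample into an A flare that was not observed. A wholly missed interior form adds no flare and keeps its days in the exposure time. From week 4 alone the size is about q false flares per subject-year: 0.02 to 0.10 for q from 2% to 10%, and more per year where follow-up was cut short.

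This rests on four assumptions: flares are judged on domain scores; worst scenario means the worst grade that the missing items allow; the bar on carrying baseline forward covers partly missing forms (it follows both cases in SAP 8.3); and q lies in the range shown. The effect is confined to the descriptive arm rates of one secondary endpoint. No hypothesis test, and neither SRI-4 nor BICLA, is affected. The change is worth making because those arm rates are the only result that this endpoint will have.

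**What to change.** In SAP 8.3, BILAG Flare index, replace the sentence on partly missing assessments with: *Observed and LOCF-imputed items will be used. A domain whose score cannot be determined from them is treated as missing for the flare index, and a worst-scenario score never counts as a flare.* Keep the worst-scenario rule for SRI-4 and BICLA. Report the number of affected domain-visits by arm.

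The cost is one sentence, a derivation flag and a small table. The downside is that a true laboratory-based flare at a visit with no sample is not counted at that visit, as already happens when the whole form is missed; if it persists, it can be counted at the next assessment. The change does not alter the exposure denominator, and it does not settle how worse or new applies to value-based items. It does stop undeterminable domains from creating flares under either reading.

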8.4 Detection of Bias

Important protocol deviations and early withdrawal from treatment and from study may bias the results of the study. The incidence of these factors will be assessed and reason for early withdrawals will be tabulated.

8.5 Outliers

Scatter plots will be examined to identify potential outliers in any of the continuous variables and frequencies of the categorical data will be examined to identify questionable values. The validity of any questionable values will be verified, and observations found to be due to data entry errors will be queried. Potential outliers that are not due to data entry error will be included in the analysis.

8.6 Distributional Characteristics

Not applicable.

8.7 Validation of Statistical Analyses

Programs will be developed and maintained, and outputs will be verified in accordance with current risk-based quality control procedures.

Tables, figures, and listings will be produced with validated standard macro programs where standard macros can produce the specified outputs.

The production environment for statistical analyses consists of Amgen-supported versions of statistical analysis software; for example, the SAS System version 9.4 or later.

9. Statistical Methods of Analysis

9.1 General Considerations

All categorical variables will be summarized using the number and percent of subjects falling into each category and all continuous variables will be summarized using mean,

standard error (SE) or standard deviation (SD), median, first quartile (Q1), third quartile (Q3), minimum, maximum, and number of subjects with observations. Safety endpoints will be summarized descriptively, including the treatment-emergent adverse events and serious adverse events, clinically significant changes in laboratory values and vital signs, and incidence of [REDACTED]. All safety analyses will be performed using the Safety Analysis Set based on subject's actual treatment received.

9.2 Subject Accountability

The study dates for the first subject enrolled, last subject enrolled, last subject's end of IP **and** last subject last visit will be presented by randomized treatment group.

The number and percent of subjects who were enrolled, randomized, received investigational product, completed investigational product, discontinued investigational product and reasons for discontinuing, completed study, discontinued study and reasons for discontinuing study will be summarized by randomized treatment group. Summary of subjects who discontinue investigational product/study due to COVID-19 control measures will be included.

9.3 Important Protocol Deviations

Important Protocol Deviations (IPDs) categories are defined by the study team before the first subject's initial visit and updated during the IPD reviews throughout the study prior to database lock. These definitions of IPD categories, subcategory codes, and descriptions will be used during the course of the study. Eligibility deviations are defined in the protocol. The final IPD list will be used to produce the summary of IPDs table and the list of subjects with IPDs. IPDs related to COVID-19 control measures will be summarized separately.

9.4 Demographic and Baseline Characteristics

The following demographic, baseline characteristics, baseline disease characteristics and baseline therapies of interest will be summarized descriptively by randomized treatment group.

Demographics:

- sex (female, male)
- age (years)
- age groups (≥ 18 to < 50 , ≥ 50 and $18 - 64$, $65 - 74$, $75 - 84$)

- race (American Indian or Alaska Native, Asian, Black or African-American, Native Hawaiian or Other Pacific Islander, White, Other)
- ethnicity (Hispanic or Latino, Not Hispanic or Latino)
- geographic region (North America [Canada and United States] + Western Europe [France, Germany, Sweden, Austria, Switzerland, and United Kingdom], ROW [Bulgaria, Czech Republic, Hungary, Italy, Poland, Russia, Turkey, Brazil, Australia, Japan, New Zealand, South Korea, Mexico, Hong Kong, Argentina, Spain, Portugal and Greece])

[figure not shown]
Baseline characteristics:

- height (cm)
- weight (kg)
- body mass index (BMI) (kg/m²)

Baseline disease characteristics:

- years since SLE diagnosis
- hSLEDAI score (continuous, ≥ 10 or < 10)
- baseline hSLEDAI organ involvement (CNS [seizure, psychosis, organic brain syndrome, visual disturbance, cranial nerve disorder, lupus headache, cerebrovascular accident], vascular [vasculitis], renal [urinary casts, hematuria, proteinuria, pyuria], musculoskeletal [arthritis, myositis], serosal [pleurisy, pericarditis], dermal [rash, alopecia, mucosal ulcers], immunologic [low complement, increased DNA binding], constitutional [fever], hematologic [thrombocytopenia, leukopenia])
- BILAG domain score (A, B, C, D, E)
 - constitutional
 - mucocutaneous
 - neuropsychiatric
 - musculoskeletal
 - cardiorespiratory
 - gastrointestinal

- ophthalmic
 - renal
 - haematological
- CLASI score (continuous, 0, > 0 to < 8, ≥ 8)
- total swollen and tender joint counts
- hand and wrist swollen and tender joint counts
- PGA score
- baseline biomarkers

Baseline medications

- **background medications (detectable vs undetectable baseline SLE SOC drug levels)**
- immuno-suppressant/immunomodulator (yes, no)
 - mycophenolate mofetil
 - azathioprine
 - methotrexate
 - hydroxychloroquine

- chloroquine
 - dapsone
 - other
- daily OCS dose (prednisone-equivalent mg/day; **continuous, 0 mg/day, > 0 to < 10 mg/day, ≥ 10 mg/day**)

9.5 Efficacy Analyses

Unless stated otherwise, the Full Analysis Set (FAS) will be used for analysis of efficacy endpoints. The efficacy analyses are summarized in [Table 9-1](#), [Table 9-2](#) and [Table 9-3](#).

The SLE efficacy assessment data (BILAG, hSLEDAI, PGA, CLASI, swollen and tender joint counts, **and SELENA-SLEDAI flare index**) will be submitted to an external independent **clinician adjudicator** with expertise in managing and assessing SLE disease and clinical trials for adjudication. The committee will adjudicate the data and determine whether the efficacy assessments are scored correctly and consistently based on the instruments' specifications.

Unless stated otherwise, the analysis of the SLE efficacy assessment data and their derived endpoints (SRI-4, BICLA, LLDAS and BILAG flare index) will be based on the data resulting from the adjudication. Additionally, **to assess the concordance between the investigators and adjudicators, the SRI-4 responses at week 16, 20, 24 and 52 based on the two sources will be cross-tabulated and** the concordance rate will be computed as the frequency of cases where the data based on the investigator's assessment and the data resulting from adjudication agree on classification of a subject as an SRI-4 responder/non-responder. If the **overall** concordance rate at week 52 is < 0.95, the **primary endpoint may be summarized** using SRI-4 responses derived based on the investigator-reported data as a sensitivity analysis.

Table 9-1. Primary Efficacy Endpoint Summary Table

Endpoint	Primary Summary and Analysis Method	Sensitivity and Supplementary Analysis
SRI-4 response at week 52	Number and percentage of subjects achieving SRI-4 response will be summarized by randomized treatment arm.	To assess different data source, the analysis may be repeated using SRI-4 responses based on the investigator data, if the concordance rate is < 0.95.

Table 9-2. Secondary Efficacy Endpoints Summary Table

Endpoint	Primary Summary and Analysis Method

 • SRI-4 response at week 24 • LLDA response at week 52 • BICLA response at week 24 • BICLA response at week 52 • SRI-4 response at week 52 with reduction of OCS to ≤ 7.5 mg/day by week 44 and sustained through week 52 in subjects with a baseline OCS dose ≥ 10 mg/day 	Number and percentage of subjects achieving response of interest will be summarized by randomized treatment arm.

 • Annualized moderate and severe flare rate (as measured by SELENA-SLEDAI Flare Index) over 52 weeks • Annualized severe flare rate (as measured by SELENA-SLEDAI Flare Index) over 52 weeks • Annualized flare rate (as measured by BILAG score designation of “worse” or “new” resulting in a B score in ≥ 2 organs or an A score in ≥ 1 organ) over 52 weeks 	Descriptive statistics will be summarized by randomized treatment arm.

 • Total tender and swollen joint count (limited to hands and wrists) $\geq 50\%$ improvement from baseline at week 12, 24, 36, and 52 in subjects with ≥ 6 tender and swollen joints involving the hands and wrists at baseline • CLASI activity score $\geq 50\%$ improvement from baseline at week 12, 24, 36, and 52 in subjects with a CLASI activity score ≥ 8 at baseline 	Number and percentage of subjects achieving response of interest will be summarized by randomized treatment arm.

• PROMIS-Fatigue score and change from baseline at week 12, 24, 36, 44, and 52• SF36v2 score and change from baseline at week 12, 24, 36, 44, and 52• LupusQoL score and change from baseline at week 12, 24, 36, 44, and 52• PtGA score and change from baseline at week 12, 24, 36, 44, and 52	Descriptive statistics will be summarized by randomized treatment arm.
---	---

Table 9-3. Exploratory Efficacy Endpoints Summary Table

Endpoint	Primary Summary and Analysis Method
REDACTED	REDACTED

